11.2 PRIMARY OUTCOME

The comparison of AI derived LVEF and sonographer measured LVEF will be determined by correlation coefficient.

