4. RESEARCH QUESTION

4.1 PRIMARY RESEARCH AIM

To determine the accuracy of AI derived LVEF compared to standard cart-based echocardiography with left ventricular ejection fraction (LVEF - the percentage of blood pumped during each heart beat) measured by biplane method, assessed by correlation coefficient.

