4.2 SECONDARY RESEARCH AIMS

To determine the accuracy of AI determined abnormal left ventricular ejection fraction (LVEF <50%) compared to standard cart-based echocardiography measurement of LVEF <50% by biplane method, determined by sensitivity, specificity, positive and negative predictive values. To determine the incremental improvement of a model to predict LVEF <50% in a population with pacemakers of the addition of AI derived LVEF, point of care NT-proBNP, or both.

To determine the proportion of participants in whom it was not possible to determine AI derived LVEF, LVEF measured by biplane method, or subjective visual estimation of LVEF.

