10 OUTCOMES

10.1 PRIMARY OUTCOME

The accuracy of AI derived LVEF compared to standard cart-based echocardiography with LVEF measured by biplane method, assessed by correlation coefficient.

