10.2 SECONDARY OUTCOMES

- The accuracy of AI derived LVEF <50% compared to standard cart-based echocardiography measurement of LVEF <50% by biplane method, determined by sensitivity, specificity, positive and negative predictive values.
- The incremental improvement of a model to predict LVEF <50% in a population with pacemakers of the addition of AI derived LVEF, point of care NT-proBNP, or both.
- The proportion of participants in whom it was not possible to determine AI derived LVEF, LVEF measured by biplane method, and subjective measurement of LVEF.

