11. STATISTICAL ANALYSIS

11.1 POWER CALCULATIONS

For this pilot study all analyses are exploratory, no statistical hypothesis has been prespecified and no formal sample size calculation has been performed. Based on previously published work assessing the accuracy of AI derived LVEF and sonographer determined LVEF we anticipate the inclusion of 150 participants would provide adequate statistical power to compare the two imaging modalities.

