11.3 SECONDARY OUTCOME

The comparison of AI derived LVEF <50% will be reported as the sensitivity, specificity, positive and negative predictive values comparing sonographer measurement of LVEF <50% by cart-based echocardiography. The improvement in the model will be reported as a comparison of the area under the curve comparing models with and without the addition of AI derived LVEF, alongside their 95% confidence intervals. The useable images and safety outcomes will be reported as proportions.

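### The primary outcome calls AI-derived LVEF accurate on a correlation coefficient alone, which measures association and not agreement with biplane LVEF

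*Protocol*

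**What the plan says.** Section 4.1 gives the primary aim as "To determine the accuracy of AI derived LVEF compared to standard cart-based echocardiography", with LVEF measured by the biplane method and a correlation coefficient as the yardstick. Section 10.1 repeats this as the primary outcome: "The accuracy of AI derived LVEF compared to standard cart-based echocardiography with LVEF measured by biplane method, assessed by correlation coefficient". Section 11.2 gives the analysis in one sentence: "The comparison of AI derived LVEF and sonographer measured LVEF will be determined by correlation coefficient". That sentence speaks of a comparison with the sonographer's measurement. The word accuracy and the biplane reference come from 4.1 and 10.1.

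None of the three sections names the type of coefficient. The protocol nowhere mentions a mean difference, limits of agreement, an intraclass or concordance coefficient, or any error in LVEF points.

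The other comparisons of the AI reading with the reference are secondary. Section 11.3 states "The comparison of AI derived LVEF <50% will be reported as the sensitivity, specificity, positive and negative predictive values", and for the prediction model "The improvement in the model will be reported as a comparison of the area under the curve". Section 11.1 states "For this pilot study all analyses are exploratory, no statistical hypothesis has been prespecified".

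**The concern.** Accuracy against a reference asks how far each AI reading lies from the biplane reading of the same patient. A Pearson coefficient asks how closely the pairs follow some straight line, and a Spearman coefficient whether they rank patients alike. Neither requires the line to be the line of equality. A device that over-reads everyone by 10 points gets the same coefficient as an unbiased one.

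Pearson r also depends on the spread of LVEF in the sample. Section 6.3 excludes known heart failure and any previous LVEF below 50%, which would be expected to narrow that spread. A modest r could then reflect case mix, not a poor device.

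So the headline figure can mislead either way: a high r is compatible with systematic misreading, and a modest r with good agreement. As written, it would be reported as accuracy.

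**Working it through.** **What needs no assumption.** For AI reading A, reference R and any constants a and b > 0, corr(a + bA, R) = corr(A, R). Pearson r is therefore blind to constant bias and to linear rescaling. Spearman is blind to any increasing transformation.

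**Inputs for the illustration.** The protocol gives no LVEF mean, SD or measurement error, so these are assumed: true LVEF normal with mean 54 and SD 9, and independent error with SD 3.5 in each method. The variance of one reading is 81 + 12.25 = 93.25. The proportion with a reference reading below 50% is Φ((50 − 54)/√93.25) = 34%, to be compared with the one third with heart failure in section 2.3.

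**1. Constant bias.** With no rescaling, r = 81/93.25 = 0.87. Lin's concordance is 2 × 81/(2 × 93.25 + bias²).

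| AI bias (points) | Pearson r | Lin's concordance | Sensitivity, LVEF <50% | Specificity |
|---|---|---|---|---|
| 0 | 0.87 | 0.87 | 78% | 89% |
| +3 | 0.87 | 0.83 | 60% | 96% |
| +5 | 0.87 | 0.77 | 48% | 98% |
| +10 | 0.87 | 0.57 | 21% | 99.8% |

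A second set of assumptions (reference mean 55, SD 8 or 10, AI error SD 4 or 6) gave r between 0.80 and 0.93, identical with and without bias. Sensitivity under +10 points fell to between 17% and 31%.

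**2. Scale error.** Let the AI reading be 50 + 0.5 × (unbiased reading − 50). No reading crosses 50, so sensitivity (78%), specificity (89%) and hence both predictive values are unchanged, and r remains 0.87. Agreement does change:
- the mean difference goes from 0 to 0.5 × (50 − 54) = −2.0;
- the SD of differences goes from √(2 × 12.25) = 4.95 to √(93.25 + 0.25 × 93.25 − 2 × 0.5 × 81) = 5.96;
- the 95% limits of agreement go from −9.7 to +9.7 to −13.7 to +9.7;
- concordance falls from 0.87 to 0.67.

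**3. Spread.** With no bias and the same error, r = SD²/(SD² + 12.25). This is 0.87, 0.84, 0.80 and 0.75 for a true SD of 9, 8, 7 and 6. The device is the same throughout.

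**4. The model comparison in 11.3.** If AI LVEF enters a regression as a linear term, refitting absorbs any shift or rescaling into the intercept and slope. The fitted ranking of patients, and so the area under the curve, is the same.

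**5. What 150 pairs would give.** With an SD of differences s, the 95% half-width is 1.96 × s/√n for the mean difference and 1.96 × s × √(1/n + 1.96²/(2(n − 1))) for each limit. With s = 5 (assumed):
- n = 150: 0.80 and 1.37 points;
- n = 100: 0.98 and 1.68 points.

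**The case against.** **The type is not named.** An absolute-agreement intraclass coefficient or a concordance coefficient is also a correlation coefficient, and a SAP might choose one. That would meet most of the objection. But it is not the plain meaning, and section 9.2 describes the NT-proBNP validation by slope, intercept and r, which points to Pearson. The measure itself is fixed in the protocol three times, so it is not merely left to the SAP.

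**The secondary outcomes cover what matters for screening.** The hypothesis in section 3 concerns detection, and "The accuracy of AI derived LVEF <50% compared to standard cart-based echocardiography measurement of LVEF <50% by biplane method" addresses it directly. This largely stands for constant bias. On the figures above, +3 points takes sensitivity from 78% to 60%, and among 150 participants gives about 20 false negatives against 4 false positives. An exact McNemar test, which the protocol does not name, would detect that imbalance in about 89% of simulated studies at one-third prevalence, and in about 44% at an assumed 10%. These outcomes still do not give the size of the bias or of individual errors across the LVEF range.

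**The scale-error example is a special case.** This is correct. Halving the scale around 52 or 54 instead of 50 lowers sensitivity to 67% or 54%, so most scale errors would leave some trace in the threshold results. The example shows only that those results can miss one.

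**The illustration is loosely anchored.** The one third in section 2.3 refers to routine pacemaker follow-up, whereas this study excludes known heart failure and any previous LVEF below 50%. Prevalence and spread may both be lower here. The percentages should be read as illustration.

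**It is an exploratory pilot.** No decision rule depends on r. This lowers the severity but does not turn association into accuracy.

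**Conclusion.** The concern holds, as something that should be fixed. On the plain reading of the coefficient, the primary analysis cannot answer the primary aim, and no other planned analysis supplies agreement in LVEF points. The invariance of r to shift and scale is exact. The sizes given (r fixed at 0.87 while sensitivity falls from 78% to 21%, and r moving from 0.87 to 0.75 on spread alone) rest on the assumed mean, SDs and errors. The conclusion would change only if the coefficient meant were an absolute-agreement one, which the protocol does not say. The consequences are contained because the study is exploratory, accuracy at the 50% threshold is prespecified, and the paired data needed for a proper analysis will exist.

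**What to change.** In sections 4.1, 10.1 and 11.2, make the primary measure the mean paired difference, AI minus biplane LVEF, with 95% limits of agreement and confidence intervals for each. Base it on participants with both readings, because the cart-based ultrasound section accepts that a biplane value will not always be obtained. Keep the correlation as a descriptive result and name its type. Leave the secondary outcomes in 10.2 unchanged.

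Optional additions are a check of whether the difference trends with the mean of the two readings, one absolute-agreement coefficient (Lin's concordance or an absolute-agreement ICC), and a pre-stated acceptable difference. A pilot without a prespecified hypothesis does not require the last of these.

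No scans or participants are added. The change alters the primary outcome, so it needs a protocol amendment. Under section 12.2 the Sponsor decides whether it is substantial, and if it is and needs NHS REC review, it must wait for that review. The planned period is July 2025 to June 2026, so recruitment may already be under way; the amendment should be dated and in place before the paired data are analysed. The result may look less favourable than r, and precision falls with every participant who lacks one of the two readings.

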11.3 SECONDARY OUTCOME

The comparison of AI derived LVEF <50% will be reported as the sensitivity, specificity, positive and negative predictive values comparing sonographer measurement of LVEF <50% by cart-based echocardiography. The improvement in the model will be reported as a comparison of the area under the curve comparing models with and without the addition of AI derived LVEF, alongside their 95% confidence intervals. The useable images and safety outcomes will be reported as proportions.

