9. STUDY PROCEDURES

9.1 BASELINE STUDY PROCEDURES

Participants will attend an appointment at the Leeds Cardiovascular Research Facility. They will have already received the Participant Information Sheet at least a week prior to their appointment, if willing to participate they will provide informed written consent. We will then collect demographic and clinical data from the participant's electronic healthcare record prior to undergoing the study procedures. Participants will undergo a routine device interrogation by an accredited cardiac physiologist as per usual clinical care to confirm device functionality and RV pacing burden $\geq 20\%$. Participants will undergo point-of-care blood testing for NTpro-BNP, a hand-held echocardiogram and a standard cart-based echocardiogram. The appointment is expected to last around one hour. Following the appointment a member of the research team will arrange their next scheduled pacemaker clinic appointment with their usual care team.

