9.2 POINT OF CARE NTPRO-BNP BLOOD TESTING

LumiraDx (LumiraDx Ltd, Cayman Islands) is a quantitative point-of-care, fingerpick blood test capable of measuring various biomarkers using a micro-sample of blood obtained from a finger prick. The LumiraDx can measure NTpro-BNP with only $20\mu\text{L}$ of blood, is highly portable, with a turn-around time of only 12 minutes – feasible within the time constraints of a standard pacemaker follow-up appointment. Their technology has been validated in a study of 659 samples compared to gold-standard commercially available laboratory equipment (Roche Cobas Elecsys proBNP II assay) and found to have comparable accuracy (slope 0.86, intercept -4.12, $r = 0.97$).

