10.3 SAFETY OUTCOMES

- The proportion of patients with a new diagnosis of at least moderate valve disease, or any other echocardiography finding which resulted in a change to patient care.

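### Section 11.3 analyses only the addition of AI derived LVEF, while sections 4.2 and 10.2 promise the gain from AI derived LVEF, from NT-proBNP, and from both

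*Protocol*

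**What the plan says.** The aim in Protocol section 4.2 is the incremental improvement of a model predicting LVEF <50% "of the addition of AI derived LVEF, point of care NT-proBNP, or both". Section 10.2 lists the same thing as a secondary outcome, "in a population with pacemakers of the addition of AI derived LVEF, point of care NT-proBNP, or both".

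The analysis is in section 11.3: "The improvement in the model will be reported as a comparison of the area under the curve", namely a "comparison of the area under the curve comparing models with and without the addition of AI derived LVEF, alongside their 95% confidence intervals". Sections 11.1, 11.2 and 11.4 say nothing on this outcome, and NT-proBNP does not appear in section 11.

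The test is a planned procedure for participants. Section 9.1 states: "Participants will undergo point-of-care blood testing for NTpro-BNP, a hand-held echocardiogram and a standard cart-based echocardiogram". Section 9.2 describes it as "feasible within the time constraints of a standard pacemaker follow-up appointment".

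**The concern.** The outcome has three parts and its analysis has one. The protocol is not leaving the comparison to a later document: it names the comparison, and names it more narrowly than the outcome it serves. An analysis plan that followed 11.3 would fall short of 10.2, and one that followed 10.2 would depart from 11.3.

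What is at stake is the study's only assessment of NT-proBNP. The primary outcome in section 10.1 is the correlation between AI derived and biplane LVEF. The other secondary outcomes in 10.2 are the diagnostic accuracy of AI derived LVEF and the proportion of participants in whom LVEF could not be determined. The safety outcome in 10.3 concerns valve disease and other echocardiographic findings. None of these uses NT-proBNP. Participants give a blood sample so that its contribution can be judged, and the stated analysis does not judge it. Leaving the contrasts open also leaves room to report whichever addition looks best.

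A smaller matter is the confidence intervals. The wording reads most naturally as one interval for each AUC. The quantity of interest is the difference between two AUCs estimated in the same people, and separate intervals do not give its precision.

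**Working it through.** **The contrasts.** The protocol states no figure for this outcome, so the main check is a comparison of texts.

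| Increment promised in 4.2 and 10.2 | Named in 11.3 |
|---|---|
| AI derived LVEF | yes |
| NT-proBNP | no |
| both | no |

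Three are promised and one is named, so 3 − 1 = 2 are uncovered. No section names the predictors in the base model, so I tried each reading.

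1. *Base without NT-proBNP.* The stated contrast is the gain from AI derived LVEF alone. The other two gains have no analysis.
2. *Base with NT-proBNP.* Those two gains are still missing. The stated contrast also changes meaning: it is now what AI derived LVEF adds over NT-proBNP, so the gain from AI derived LVEF alone is missing too.
3. *Several pairs of models, with and without AI derived LVEF, at both levels of NT-proBNP.* Each comparison still varies only AI derived LVEF. NT-proBNP against base, and both against base, remain unnamed.

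**The intervals (illustration only).** The inputs here are assumptions apart from N = 150, which is the planned sample size. The AUCs are taken as 0.80 and 0.88, and the correlation r between the two AUC estimates as 0.3 to 0.9. Cases are taken as 15, 30 or 50. Section 2.3 reports heart failure in one third of routine clinic patients (150 / 3 = 50), and section 6.3 excludes known heart failure and any earlier LVEF <50%, so lower counts are plausible.

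The Hanley-McNeil variance of an AUC A with n₁ cases and n₀ non-cases is [A(1−A) + (n₁−1)(q₁−A²) + (n₀−1)(q₂−A²)] / (n₁n₀), where q₁ = A/(2−A) and q₂ = 2A²/(1+A). The half-width for the difference is 1.96·√(s₁² + s₂² − 2r·s₁s₂).

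With 30 cases, s₁ = 0.0511 and s₂ = 0.0419. At r = 0.3 the half-width is 1.96·√(0.00261 + 0.00175 − 0.00128) = 0.109.

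| Cases | Separate interval, AUC 0.80 | Separate interval, AUC 0.88 | r = 0.3 | r = 0.5 | r = 0.7 | r = 0.9 |
|---|---|---|---|---|---|---|
| 15 | 0.662–0.938 | 0.766–0.994 | 0.151 | 0.128 | 0.100 | 0.061 |
| 30 | 0.700–0.900 | 0.798–0.962 | 0.109 | 0.092 | 0.073 | 0.044 |
| 50 | 0.719–0.881 | 0.815–0.945 | 0.087 | 0.074 | 0.058 | 0.036 |

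The last four columns are half-widths for the 0.08 gain. With 30 cases, the same two separate intervals are compatible with an interval for the gain of −0.029 to 0.189 (r = 0.3) or 0.036 to 0.124 (r = 0.9).

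Pairing does not guarantee a clear answer. At r = 0.5 and 0.7, three of the six scenarios have a half-width above 0.08 and so include zero: 15 cases at both correlations, and 30 cases at r = 0.5.

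As a check on the range of r, I simulated 1000 data sets with 30 cases among 150. They compared one normal marker (true AUC 0.80) with that marker plus an independent second one (true combined AUC 0.88). The mean DeLong correlation was about 0.64 and the mean paired half-width about 0.07.

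**The case against.** The strongest reply is that 11.3 is an incomplete summary and not a decision to drop NT-proBNP. Section 10.2 still lists all three additions, and 11.3 refers back to that outcome, so a careful analyst would report them anyway. The plural in 11.3 could also cover a clinical model and a clinical-plus-NT-proBNP model, each with and without AI derived LVEF. All four AUCs would then be printed and a reader could subtract. Part of this stands: the omission may well be inadvertent, and 10.2 does not withdraw anything. But that reading still does not name the NT-proBNP or combined contrasts, and printed AUCs do not supply intervals for the differences.

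A second reply is that the type of interval is detail for an analysis plan, which may exist. That largely stands. The sentence does not exclude an interval for the difference; it only fails to ask for one. The point is therefore secondary, and the figures above rest wholly on assumed inputs. The main finding does not depend on them.

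Third, the sections could be reconciled the other way, by narrowing 4.2 and 10.2. That would be consistent, but it would leave a blood test in the protocol that no outcome uses.

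Finally, the impact is small: section 11.1 declares all analyses exploratory. That is true, and it limits the weight of the point without removing the mismatch.

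**Conclusion.** The concern holds. At least two of the three promised increments have no stated analysis, and this does not depend on how the base model is read or on any assumed number. The consequence is limited to one secondary outcome of an exploratory pilot. No sample size or hypothesis rests on it, and it can be put right before analysis without new data. It should be corrected, because this is the only outcome in which NT-proBNP is evaluated. The interval point is a clarification worth making in the same edit. Its size depends on the AUCs, case counts and correlations assumed above.

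**What to change.** Replace the sentence on model improvement in section 11.3, for example with:

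> The gain in predicting LVEF <50% will be reported as the difference in area under the curve between a base model containing neither marker and that model extended by (i) AI derived LVEF, (ii) NT-proBNP and (iii) both. All models will be fitted in the same participants, and each difference will have a 95% confidence interval that allows for the pairing.

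A base model with neither marker follows from the outcome being defined by what each marker adds. The interval can come from a bootstrap or the DeLong method. The base-model covariates can be left to the statistical analysis plan. Comparing the combined model with each single marker, and correcting for optimism, are optional.

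Section 10.2 expects some participants to have no obtainable AI derived LVEF, so fitting in the same participants will exclude some, and the number should be reported.

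The cost is one sentence and two further model fits on data already collected. The downside is a few more exploratory contrasts, some with wide intervals.

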11.4 DEFINITION OF THE END OF THE STUDY

The end of the study will occur at the completion of the final participant's research visit.

12 ETHICAL AND REGULATORY CONSIDERATIONS

All investigators and study site staff will comply with the requirements of the Data Protection Act 2018 with regards to the collection, storage, processing and disclosure of personal information and will uphold the Act's core principles.

12.1 ASSESSMENT AND MANAGEMENT OF RISK

This study enhances usual clinical care, and it is likely that the intervention of echocardiographic screening will result in new findings and changes to patient management. One potential issue is the discovery of important heart muscle weakness, or other abnormal findings on echocardiography. All new findings will be reviewed by the Chief Investigator, or delegated to another Investigator in his absence, and managed according to current clinical practice recommendations. We will report as a safety outcome the proportion of patients with a new diagnosis of at least moderate valve disease, or any other echocardiography finding which resulted in a change to patient care - whether this be a change in treatment, or a referral for further tests. We will inform the patient's General Practitioner of any abnormal findings and the action we have taken as a result of this. Cardiac physiologists work within the National Health Service as technicians who perform echocardiography and as part of their role will interpret the images and measure heart structure and function. The Chief Investigator is a Cardiologist who is familiar with echocardiography and appropriately trained to interpret and action the results. Any changes to participant management will fall outside of this study, and the Chief Investigator will either action these changes himself, or refer to the clinical team within the National Health Service, as appropriate.

